#### 8.1.1. Discontinuation of Inadvertently Enrolled Patients/Subjects

If the sponsor or investigator identifies a patient who did not meet enrollment criteria and was inadvertently enrolled, a discussion must occur between the Lilly clinical pharmacologist or CRP and the investigator to determine if the patient may continue in the study. If both agree it is medically appropriate to continue, the investigator must obtain documented approval from the Lilly clinical pharmacologist or CRP to allow the inadvertently enrolled patient to continue in the study with or without continued treatment with IP.

### 8.2. Discontinuation from the Study

Patients/subjects will be discontinued under the following circumstances:

- Enrollment in any other clinical study involving an IP or enrollment in any other type of medical research judged not to be scientifically or medically compatible with this study
- Participation in the study needs to be stopped for medical, safety, regulatory, or other reasons consistent with applicable laws, regulations, and good clinical practice (GCP)
- Investigator Decision
  - the investigator decides that the patient/subject should be discontinued from the study

- if the patient/subject, for any reason, requires treatment with another therapeutic agent that has been demonstrated to be effective for treatment of the study indication, discontinuation from the study occurs prior to introduction of the new agent
- Subject Decision
  - the patient/subject, or legal representative, requests to be withdrawn from the study.
- Sponsor Decision
  - Lilly stops the study or stops the subject's participation in the study for medical, safety, regulatory, or other reasons consistent with applicable laws, regulations, and GCP
- Suicidal Ideation and/or Behavior
  - When a subject discontinues from a study due to suicidal ideation and/or behavior, the same follow-up procedures can be used as would be done for discontinuation due to any other AEs leading to discontinuation. It is not necessary to collect additional information (except what is already requested on the C-SSRS, the Self-Harm Supplement Form, and the Self-Harm Follow-up Form).
  - Investigators are responsible for monitoring the safety of patients/subjects who have entered this study and for alerting Lilly or its designee to any event that seems unusual, even if this event may be considered an unanticipated benefit to the patient/subject.
  - The investigator is responsible for the appropriate medical care of patients/subjects during the study.
  - The investigator remains responsible for following, through an appropriate health care option, AEs that are serious or that caused the patient/subject to discontinue before completing the study. The patient/subject should be followed up until the event is resolved or explained. Frequency of follow-up evaluation is left to the discretion of the investigator
- Adverse event
  - if a clinically significant event (CSE) occurs, the IP has to be discontinued and appropriate measures taken. Lilly or its designee should be alerted immediately. A CSE will be defined as a moderate to severe AE, abnormal clinical sign, or clinical laboratory finding that may pose a risk to the wellbeing of the subject. Refer to Safety Section (Section 9.4).
  - A clinically significant systemic hypersensitivity reaction occurs following administration of the IP (for example, drug-related symptomatic bronchospasm,

allergy-related edema/angioedema, or hypotension) that requires parenteral medication, does not respond to symptomatic medication, or results in clinical sequelae or an anaphylactic reaction.

Following the investigator's determination that CSE criteria have been met and the investigator's judgment of relatedness to the IP is documented, a decision will be made between the investigator and Lilly or its designee regarding subject discontinuation.

The nature of any conditions, clinical signs or symptoms, or abnormal laboratory values present at the time of discontinuation and any applicable follow-up procedures will be documented.

Refer to the Schedule of Activities (Section 2) for data to be collected at the time of discontinuation and follow-up.

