### **5.1.3. Part C (Single-Dose Design in Patients with Psoriasis)**

One planned single-dose cohort will be enrolled to receive IV administration of LY3316531 with the option of 2 subsequent cohorts where the dose levels and route of administration (SC or IV) would be determined after reviewing the data from the first IV cohort.

The first cohort is planned to receive 300 mg of LY3316531 pending the analysis of available safety data from Part A. The safety scenarios for AEs, SAEs, and adverse laboratory abnormalities described in Section 7.4.2 that would prevent dose escalation in Parts A and B are the same that would prevent initiation of Part C. The actual starting dose and expected exposure will not exceed the dose/exposure that is concurrently being evaluated in Part A. Any available preliminary PK data from Cohorts 1, 2, and 3 (through Day 29) in Part A will be considered in the decision to initiate Part C as well.

Similarly, the dose for the optional cohorts will be determined based on cumulative data from previous cohorts, but will not exceed 2000 mg of LY3316531. Section 7.4.1 provides detailed information on how dose levels for the 2 optional cohorts will be determined and when the cohorts will begin enrollment procedures.

All patients who respond to LY3316531 treatment by exhibiting at least 50% reduction from baseline Psoriasis Area and Severity Index (PASI) score at Week 12 (Visit 11; Day 85) can enter an extended follow-up period for up to 52 weeks post-treatment administration (see Section 2.3). Other subjects who do not meet the above criterion for PASI reduction should be considered for discontinuation from the study at Week 16 (Visit 12; Day 113). Exceptions could be considered after a discussion between the sponsor and investigator.

A patient's participation is considered as complete if he/she received the study drug and completes all activities up to and including at least Day 85. Patients may be replaced if PK or PD data are not collected up to and including Day 85.

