## 7.4. Dose Modification

### 7.4.1. Dose Decision (Part C)

The decision to initiate the first patient cohort in Part C will be based on the trial-level safety review for Cohort 3; however, any available preliminary PK data from Cohorts 1, 2, and 3 (through Day 29) in Part A will be considered as well. Progression to the optional cohorts in Part C will occur when at least 4 weeks of clinical activity data (PASI scores) are available from at least 7 patients in the preceding cohort. In addition to the PASI scores, any available PK and applicable safety data from Part A will be considered for determining the dose for the optional patient cohorts. Dosing at the current level and further dose escalation will be discontinued if any of the scenarios described in Section 7.4.2 occur.

CCI

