## 10. Statistical Considerations and Data Analysis

### 10.1. Sample Size Determination

The sample size for each cohort is customary for the first-in-human study in which formal power analyses is not necessary to address the objectives associated with safety, tolerability, PK, and/or PD assessments. Approximately 86 patients/subjects are planned for enrollment; however, up to 102 subjects may be enrolled to allow for replacement of subjects and any additional dose cohorts (Parts A, B, and C).

Subjects/patients who withdraw from the study before completing the Day 57 (Part A) or Day 85 (Parts B and C) assessment may be replaced if necessary to have the planned number of subjects/patients complete a dose cohort. A replacement subject/patient will be assigned the same treatment as the subject/patient he or she replaces (Parts A, B, and C).

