### 10.3. Statistical Analyses

Statistical analysis of this study will be the responsibility of Eli Lilly and Company or its designee.

Pharmacokinetic/PD analyses (CGRP target engagement) will be conducted on data from all patients/subjects who receive at least 1 dose of the IP and have evaluable PK.

Clinical activity and PD analyses will be conducted for all patients with psoriasis who receive the study drug (Part C only).

Safety analyses will be conducted for all enrolled patients/subjects, whether or not they completed all protocol requirements.

All protocol deviations that occur during the study will be considered for their severity/impact and will be taken into consideration when subjects are assigned to analysis populations prior to database lock and unblinding. Details of subject assignment to the analysis populations will be listed.

The placebo data from all cohorts will be pooled across all dose-escalation cohorts for the purpose of analysis.

Additional exploratory analyses of the data will be conducted as deemed appropriate. Study results may be pooled with the results of other studies for population PK analysis purposes to avoid issues with post hoc analyses and incomplete disclosures of analyses.

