#### **10.3.3. Pharmacodynamic Analyses and Clinical Activity**

Clinical activity and PD data obtained will be documented in the study report by dose, plasma drug concentrations, and time from dose. However, the data collected at the visits leading up to and including the Week 4 visit will be the data used for evaluation of changes in clinical activity and PD measures. Figures showing values of potential PD markers versus time will be created for each dose, with a line for each patient. Absolute percentage change from baseline for all will be summarized by providing the mean, standard deviation, median, minimum, and maximum for each cohort and overall for each sample day/time combination and maximum over the entire study. Data may be log-transformed prior to summarizing if necessary. The interpatient and intrapatient variability in human PD responses may also be assessed if appropriate.

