9.4 Pharmacodynamic Assessment

9.4.1 Pharmacodynamic Analysis

The sPGA, PASI, and percent BSA are considered PD (efficacy) measures of disease activity in this study. Table 2 includes the description and derivation of the efficacy outcomes.

Table 2 Description and Derivation of Efficacy Outcomes (PD measures)

| Measure | Description | Variable | Derivation / Comment | Imputation Approach if with Missing Components |
|---------|--|------------|--|--|
| sPGA | Static Physician Global Assessment (sPGA): the physician's global assessment of the patient's psoriasis (Ps) lesions at a given time point (European Medicines Agency [EMA] 2004). Plaques are assessed for induration, erythema, and scaling, and an overall rating of psoriasis severity is given using the anchors of clear (0), minimal (1), mild (2), moderate (3), severe (4), or very severe (5). | sPGA (0) | Score is clear (0) | Single item, missing if missing |
| | | sPGA (0,1) | Score is clear or minimal (0 or 1) | Single item, missing if missing |
| PASI | Psoriasis Area and Severity Index (PASI): combines assessments of the extent of body-surface involvement in 4 anatomical regions (head and neck, trunk, arms, and legs) and the severity of scaling (S), redness (R), and plaque induration/infiltration (thickness, T) in each region, yielding an overall score of 0 for no psoriasis to 72 for the | PASI 75 | A clinically meaningful response; at least a 75% improvement in PASI score from baseline | Missing if baseline or observed value is missing |
| | | PASI 90 | Higher level of clearance; at least a 90% improvement in PASI score from baseline | Missing if baseline or observed value is missing |
| | | PASI 100 | Complete resolution of plaque Ps; a 100% improvement in PASI score from baseline | Missing if baseline or observed value is missing |

| Measure | Description | Variable | Derivation / Comment | Imputation Approach if with Missing Components |
|---------|--|--|--|--|

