9.4.1.2 Psoriasis Area Severity Index (PASI)

The proportion of patients who achieve PASI 75 (at least a 75% improvement from baseline in PASI score), PASI 90 (at least a 90% improvement from baseline in PASI score) and PASI 100 (a 100% improvement from baseline in PASI score) will be summarized over time using descriptive statistics. In addition, the change from baseline and percent improvement from baseline will be summarized over time using descriptive statistics. A by-patient listing of PASI will be provided. The listing will include patient number, treatment, timepoint, PASI total score, change from baseline, percent improvement and the PASI response.

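### Part C patients who leave because they need another psoriasis agent drop out of the later PASI and sPGA response proportions, which biases observed response upward

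*Protocol*

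**What the plan says.** **Exit.** Protocol 8.2 covers a patient who needs another agent shown to be effective for the study indication, whatever the reason: "discontinuation from the study occurs prior to introduction of the new agent".

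**Replacement.** Protocol 5.1.3 (repeated in SAP 5.3) states: "Patients may be replaced if PK or PD data are not collected up to and including Day 85". Protocol 10.1 and SAP 7 add that those who withdraw before Day 85 in Part C "may be replaced if necessary to have the planned number of subjects/patients complete a dose cohort". Neither place makes an exception for lack of effect.

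**Analysis set.** Protocol 10.3 and SAP 8 include every dosed psoriasis patient in the clinical activity analysis.

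**Missing values.** For PASI 75, 90 and 100, SAP Table 2 says "Missing if baseline or observed value is missing". For sPGA (0) and (0,1) it likewise leaves an absent score missing. SAP 9.4.1.2 says that the PASI proportions "will be summarized over time using descriptive statistics", and SAP 9.4.1.1 treats sPGA the same way. No non-responder rule is given.

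**Timing.** For judging whether activity has changed, Protocol 10.3.3 sets a window: "the data collected at the visits leading up to and including the Week 4 visit will be the data used for evaluation". Under Protocol 7.4.1, optional cohorts may open when "at least 4 weeks of clinical activity data (PASI scores) are available from at least 7 patients in the preceding cohort".

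**The concern.** The reason for leaving is closely tied to the outcome being summarised. A patient who needs another psoriasis treatment has, in most cases, not responded adequately. After exit there is no PASI or sPGA value at the remaining visits, and the SAP counts an absent value neither for nor against response. The proportion at those visits is then taken over patients who did well enough to stay.

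Cohorts have 7 to 8 patients and no placebo arm, so one or two uncounted failures move the percentage visibly. The response tables will inform how active the drug appears. The synopsis also says that Cohort 1 PASI results may point to a lower dose if activity is high or a higher dose if it is minimal. The question is how much of this the exit and missing-data rules can affect, and at which visits.

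**Working it through.** **1. The plan's own figures.** Planned enrolment is 46 + 16 + 24 = 86 and the maximum is 52 + 20 + 30 = 102; both match Protocol 10.1. Part C has 30 − 24 = 6 spare places, an average of 2 per cohort if all three cohorts open. The documents state no response rate, exit rate or power for Part C.

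**2. One cohort.** Inputs: 8 treated (Protocol Table FFAA.5.1); 4 responders and 2 exits for another agent (assumed).

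- Exits counted as non-responders: 4/8 = 50%.
- Exits left missing: 4/(8 − 2) = 4/6 = 67%.
- With one exit instead of two: 4/7 = 57%.

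If the two who left are replaced and both replacements complete, the rate among the 8 completers lies between 4/8 = 50% and 6/8 = 75%. Over all 10 treated, with the exits counted as failures, it lies between 4/10 = 40% and 6/10 = 60%.

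**3. Expected size.** Let p be the true response rate among treated patients and d the share of treated patients who leave as failures. Observed response is then about p/(1 − d). This was compared with a simulation of 200,000 cohorts, without replacement (8 treated) and with it (enrolling until 8 complete or 10 are treated).

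| p | d | p/(1 − d) | Observed, no replacement | Observed, with replacement | Exits as failures, no replacement | Exits as failures, with replacement |
|---|---|---|---|---|---|---|
| 0.50 | 0.125 | 57.1% | 57.2% | 57.2% | 50.0% | 50.5% |
| 0.50 | 0.25 | 66.7% | 66.6% | 66.7% | 49.9% | 50.5% |
| 0.30 | 0.25 | 40.0% | 40.1% | 40.1% | 30.1% | 30.4% |

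Replacement changes the observed-case rate by at most 0.1 point. The upward shift is already there without it.

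The same result follows if q is the share of non-responders who leave, so that d = (1 − p)q. For q = 0.2 and 0.4, p/(1 − (1 − p)q) gives:

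- p = 0.5: 0.5/0.90 = 0.556 and 0.5/0.80 = 0.625
- p = 0.3: 0.3/0.86 = 0.349 and 0.3/0.72 = 0.417
- p = 0.7: 0.7/0.94 = 0.745 and 0.7/0.88 = 0.795

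A simulation with up to two replacements gives 0.554 and 0.625, 0.349 and 0.419, and 0.746 and 0.796, the same to within simulation error and small-cohort effects.

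**4. What replacement does change.** At p = 0.5, q = 0.2 and 0.4 give d = 0.10 and 0.20. The chance that 8 treated patients all complete is 0.9^8 = 43% or 0.8^8 = 17%. With up to 10 treated, the chance of at least 8 completers is 93% or 68% (binomial). The cohort looks full more often, and the loss shows less in the number of completers.

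**5. Which visits.** The activity evaluation in Protocol 10.3.3 and the condition in 7.4.1 both rest on data to Week 4. An exit after Week 4 leaves those data intact and affects only the later PASI and sPGA response tables. An exit before Week 4 can matter, because 7.4.1 does not say how such a patient is taken into account.

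**The case against.** A reader might infer that failures are swapped for new patients and that this inflates the cohort's activity. The documents do not support that. Every dosed patient stays in the clinical activity set, SAP 9.1 lists data up to withdrawal, and replacement is discretionary. The inflation is the same with no replacement at all, so barring replacement would leave it in place.

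A reader might also infer that the loss is hidden and that exits up to Day 85 distort the dose choice for optional cohorts. Neither holds as stated. Protocol 10.2.1 requires every discontinuation to be reported, with the reason if known, and Part C is open-label, so those who decide will know of any exit. The 7-patient condition sets when progression may occur; it does not say that other patients' data are ignored. Protocol 5.1.3 bases optional-cohort doses on cumulative data. In a cohort of 8, one early exit still leaves 7 without replacement.

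Finally, the primary endpoint is safety, activity is descriptive without inference, and no power is claimed. All of this stands, and it limits the consequence. It does not answer the missing-data point: membership of an all-treated set does not help at a visit where the patient's response is missing. The early-discontinuation visit does not help either, even if PASI is scored there, because no rule carries that score to later visits.

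**Conclusion.** The point holds as a minor missing-data gap. Mandatory exit combined with missing responses left as missing biases the PASI and sPGA response proportions upward at visits after exit. With one or two exits among 8 treated and 4 responders, 50% reads as 57% or 67%. In expectation, a true 50% reads as 57% to 67% if 12.5% to 25% of treated patients leave as failures, and a true 30% reads as 40% if 25% do.

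Three assumptions carry these figures. The exit rates are illustrative. Those who leave for another psoriasis agent are taken to be non-responders. The per-visit denominator is taken to be patients with an observed value, which is the natural reading of Table 2 but is not written out in the SAP.

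Replacement adds only that the shortfall in completers is less visible. The Week 4 evaluation and the optional-cohort reading are exposed only to exits before Week 4, and the documents give no basis for estimating how many there would be.

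**What to change.** In SAP Table 2 and SAP 9.4.1.1 and 9.4.1.2:

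- Count a patient who leaves because another psoriasis agent is needed as a non-responder for PASI 75, 90 and 100 and for sPGA (0) and (0,1) at every scheduled visit after exit.
- Use all treated Part C patients in the cohort as the denominator.
- Keep the observed-case summary as supportive.
- Show replaced patients and their replacements separately, with reasons.

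When the 4-week PASI data are reviewed under Protocol 7.4.1, present any earlier exits of this kind alongside them.

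The clinical rule on other therapy, the permission to replace and the dose-decision rule stay as they are. The cost is SAP wording, one additional display and recording of the reason for exit. The descriptive response rates may become slightly less favourable.

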### **8.3. Patients/Subjects Lost to Follow-up**

A patient/subject will be considered lost to follow-up if he or she repeatedly fails to return for scheduled visits and is unable to be contacted by the study site. Site personnel are expected to make diligent attempts to contact patients/subjects who fail to return for a scheduled visit or were otherwise unable to be followed up by the site.

## 9. Study Assessments and Procedures

Section 2 lists the Schedule of Activities, detailing the study procedures and their timing (including tolerance limits for timing).

Appendix 2 lists the laboratory tests that will be performed for this study.

Appendix 5 provides a summary of the maximum number and volume of invasive samples, for all sampling, during the study.

Unless otherwise stated in subsections below, all samples collected for specified laboratory tests will be destroyed within 60 days of receipt of confirmed test results. Certain samples may be retained for a longer period, if necessary, to comply with applicable laws, regulations, or laboratory certification standards.

### 9.1. Efficacy Assessments

This section is not applicable for this study.

### 9.2. Adverse Events

Investigators are responsible for monitoring the safety of patients/subjects who have entered this study and for alerting Lilly or its designee to any event that seems unusual, even if this event may be considered an unanticipated benefit to the patient/subject.

The investigator is responsible for the appropriate medical care of patients/subjects during the study.

Investigators must document their review of each laboratory safety report.

The investigator remains responsible for following, through an appropriate health care option, AEs that are serious or otherwise medically important, considered related to the IP or the study, or that caused the patient/subject to discontinue the IP before completing the study. The patient/subject should be followed until the event resolves, stabilizes with appropriate diagnostic evaluation, or is reasonably explained. The frequency of follow-up evaluations of the AE is left to the discretion of the investigator.

After the ICF is signed, study site personnel will record, via electronic data entry/designated data transmission methods, the occurrence and nature of each patient/subject's preexisting conditions, including clinically significant signs and symptoms of the disease under treatment in the study. Additionally, site personnel will record any change in the condition(s) and the occurrence and nature of any AEs.

The investigator will interpret and document whether or not an AE has a reasonable possibility of being related to study treatment, or a study procedure, taking into account the disease, concomitant treatment, or pathologies.

A "reasonable possibility" means that there is a potential cause and effect relationship between the IP, study device, and/or study procedure and the AE.

Planned surgeries and nonsurgical interventions should not be reported as AEs unless the underlying medical condition has worsened during the course of the study.

If a patient's/subject's IP is discontinued as a result of an AE, study site personnel must report this to Lilly or its designee via electronic data entry/designated data transmission methods.

